5. Patient affiliated with a social security system

Exclusion criteria:

1. Minors, pregnant or breastfeeding women
2. Obstetric procedures
3. Surgeries under Local Anesthesia (LA) or peripheral nerve block
4. Procedures performed outside an interventional room (e.g., operating theater or interventional radiology)
5. Procedures related to previous surgical complications
6. Patients reoperated during follow-up (no double inclusion for the second surgery)
7. Organ transplantation
8. Patients already intubated preoperatively
9. Outpatient surgery
10. Refusal to participate or inability to provide informed consent
11. Persons deprived of liberty or adults under guardianship
12. Participation in another interventional study.

Primary endpoint:

Occurrence of acute respiratory failure (ARF) within 7 postoperative days during hospitalization, validated by the blinded adjudication committee with respect to the randomization arm.

Secondary endpoints:

Assessment of the safety and tolerability of the strategy under study:

- Discomfort or intolerance to NIV, defined as the inability to achieve the target of 6 to 8 hours per day due to premature termination of sessions caused by intolerance, despite proper implementation of NIV, including excessive leaks when these are the reason for stopping sessions
- Skin lesions at contact points between the interface and the patient's skin
- Anastomotic suture dehiscence (digestive or bronchial) when caused by a total pressure (PEEP + IPAP) > 20 cmH₂O
- Gastric distension defined as aeric distension of the gastric air pocket evidenced by imaging or gastric tube aspiration
- Occurrence of aspiration of secretions or vomit whose evacuation was hindered by the NIV mask

Any ARF must lead to investigation of its etiology using appropriate examinations:

Infectious pneumonia defined by a Modified Clinical Pulmonary Infection Score (CPIS) > 6, with microbiological thresholds of culture concentrations >10³ CFU/ml for a protected distal sample, >10⁴ CFU/ml for bronchoalveolar lavage, and >10⁶ CFU/ml for tracheal aspiration

The Modified Clinical Pulmonary Infection Score (modified CPIS)

CPIS Points	0	1	2
Tracheal secretions	Rare	Abundant	Abundant + purulent
Chest X-ray infiltrates	No infiltrate	Diffused	Localized
Temperature, °C	≥36.5 and ≤38.4	≥38.5. and ≤38.9	≥39 or ≤36.4
Leukocytes count, per mm ³	≥4,000 and ≤11,000	<4,000 or >11,000	<4,000 or >11,000 + band forms ≥500

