Statistical analyses will be performed using R software and IBM SPSS.

A total of 266 patients are planned for inclusion, divided into two balanced groups.

DESCRIPTION OF PLANNED STATISTICAL METHODS:

Research Protocol

Patients will be analyzed on an intention-to-treat basis and then per-protocol.

Intention-to-treat analysis: all patients included in the study for whom outcome data are available will be considered in the analysis according to their randomization group. No imputation method will be used in case of missing data.

If organizational constraints prevent the patient from receiving prophylactic NIV (despite inclusion in the corresponding intervention arm), the patient will remain in their randomization arm for the entire study duration, and their data will be analyzed on an intention-to-treat basis.

Per-protocol analysis excludes patients for whom the initial protocol was not fully adhered to. Only patients who followed the protocol will be considered in the analyses, within the arm to which they were originally randomized.

The analysis will focus on the primary endpoint to determine whether randomization to the "PPC prevention strategy" arm leads to a reduction in PPC frequency compared to the control group. Effect size and number needed to treat will be calculated.

Similarly, for secondary endpoints, significant differences between the two groups will be sought in terms of:

- a) Safety and tolerability of the strategy under study (see safety assessment parameters)
- b) Mortality during hospitalization
- c) Patient reintubation
- d) Length of stay and duration of invasive or non-invasive mechanical ventilation

Description of the overall analysis method

The significance threshold is set at 0.05, and all tests will be two-sided. For qualitative variables, results will be reported as counts and percentages. For quantitative variables, results will be reported as means and standard deviations in case of normal distribution, and as medians with 25th and 75th percentiles in the absence of a Gaussian distribution. Normality of continuous variables will be assessed using the Kolmogorov-Smirnov test.

A simple descriptive analysis will be performed on the entire study population and by subgroups. This description will include sociodemographic data, medical history, ongoing treatments, etc.

A qualitative and quantitative analysis of missing data will be performed. No imputation of missing data is planned for the endpoints.

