Study of Associations (Qualitative and/or Quantitative Variables):

For each parameter of interest, a bivariate analysis will be performed, possibly complemented by a multivariate analysis adapted to the outcome variable to explore potential associations.

For bivariate analyses, the use of parametric or non-parametric tests will depend on sample size and/or variable distribution. The significance threshold is set at 0.05, and all tests will be two-sided.

The statistical test used will be Pearson's Chi-square test (or Fisher's exact test) for qualitative variables. For quantitative variables, the statistical tests used will be ANOVA or the non-parametric Kruskal-Wallis test.

The association between each presumed risk factor and the parameter of interest will be estimated using the relative risk (RR) and its 95% confidence interval.

A multivariate logistic regression analysis will estimate the adjusted RR and its 95% confidence interval for each retained factor (conservative threshold of 0.20 in univariate analysis).

Early Mortality:

Overall survival is defined as the time between the date of operating room discharge and the date of death if the patient dies within 7 days, or the end of study follow-up at Day 7. The Kaplan-Meier method will be used to estimate survival rates and plot survival curves. The Log-Rank test will be used to compare survival curves. Event-free survival is defined as the time between operating room discharge and the date of occurrence of the event (PPC) or the date of last follow-up if censored.

A semi-parametric Cox proportional hazards regression model will estimate for each variable the crude association (Hazard Ratio, HR) between the factor studied and death (bivariate analysis), then the adjusted HR in multivariate analysis.

The significance threshold for including other variables in the multivariate analysis will be 0.20. If several candidate variables are redundant, the most representative variable will be retained for the model.

Subgroup Analyses (Exploratory):

Subgroup analyses will address the occurrence of endpoints:

- According to patient characteristics at inclusion (medical history, ARISCAT score components, type of surgery, and planned anesthetic technique).
- The subgroup of patients receiving NIV as curative (under conditions noted at session start) will be compared to the group receiving NIV only prophylactically in terms of outcome at Day 7.

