Protocol deviations will be identified and measured. Dual analysis—intention-to-treat and per-protocol—will assess the impact of protocol deviations on study results.

SELECTION OF PATIENTS FOR ANALYSIS:

All patients included in the study, meeting all inclusion criteria and presenting no exclusion criteria, will be included in the analyses of available endpoints according to their case report forms.

See Criteria for Premature Discontinuation of a Participant's Involvement in the Study:

- **Withdrawal of consent:** Data collected will not be included in the intention-to-treat analysis.
- **Discontinuation by the investigator:** Data already collected will be used in the analyses unless the subject withdraws consent.
- **Lost to follow-up:** Data collected for subjects lost to follow-up will be used in the analyses unless the subject withdraws consent.
- **Organizational impossibility to receive prophylactic NIV (inclusion in the corresponding intervention arm):** The patient will be included in the intention-to-treat analysis and followed under the same conditions as in the control arm.

RANDOMIZATION

High-risk patients with an ARISCAT score ≥ 45 will be randomized upon inclusion in the study during the preoperative period (consultation or pre-anesthesia visit, and no later than the day of surgery before anesthesia begins).

Treatment allocation will be performed through centralized computerized electronic randomization by minimization into two groups (1:1), with stratification by center, sex, age, preoperative SpO₂, presence of respiratory infection within the previous month, anemia, surgical incision (upper abdominal or intrathoracic), expected surgery duration (≤ 2 h, 2–3h, > 3 h), and procedure urgency.

F) Planned Duration of the Trial

Inclusion period:	30 months
Treatment period:	48 hours
Follow-up period:	7 days
Total duration of the trial (including follow-up):	30.5 months

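### Safety and tolerability of NIV have no exposed-patient analysis: the per-protocol set removes intolerant patients, and ITT does not give the harm rate among NIV recipients

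*Combined protocol and SAP*

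**What the plan says.** Section E, under the description of planned statistical methods, sets the analysis populations: "Patients will be analyzed on an intention-to-treat basis and then per-protocol". Safety and tolerability is item a) in the list of secondary endpoints to be compared between the two groups. It is given no population of its own, and no safety or as-treated set is defined elsewhere in the text.

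The per-protocol rule is strict and has no threshold: "Per-protocol analysis excludes patients for whom the initial protocol was not fully adhered to". It continues: "Only patients who followed the protocol will be considered in the analyses, within the arm to which they were originally randomized".

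Section C (secondary endpoints) defines discomfort or intolerance as "inability to achieve the target of 6 to 8 hours per day due to premature termination of sessions caused by intolerance". Section D (therapeutic regimen, duration of treatment) gives the same daily hours as the aim of prophylactic NIV, for at least 24 hours.

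For patients allocated to NIV who cannot be given it for organisational reasons, Section E (selection of patients for analysis) says: "The patient will be included in the intention-to-treat analysis and followed under the same conditions as in the control arm".

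Curative NIV is expected. Section C counts days of therapeutic as well as prophylactic NIV, and the exploratory subgroup analyses compare patients given curative NIV with those given prophylactic NIV only. Neither place says in which arm curative NIV may occur, or how often.

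**The concern.** Safety and tolerability is the first secondary objective. A reader of the results will want to know how often patients who start prophylactic NIV cannot tolerate it or are harmed by it. Neither planned set answers that. One drops patients because they had the event. The other counts patients who were never at risk of it.

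The per-protocol result is the more serious of the two. A tolerability rate near zero that arises from how the set is built could be read as evidence that NIV is well tolerated.

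**Working it through.** The plan states no expected harm rate, NIV delivery rate or curative-use rate, so it has no figure on this point to reproduce. Step 1 rests on the text alone. Steps 2 to 4 use assumed inputs, labelled as such.

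**Step 1. Per-protocol and intolerance.** Three rules, side by side:

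| Rule | Place | Content |
|---|---|---|
| Endpoint | Section C, secondary endpoints | Intolerant = 6–8 h/day not reached because sessions were stopped |
| Regimen | Section D | 6–8 h/day is the aim of prophylactic NIV |
| Set | Section E, planned methods | Full adherence required |

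A patient who meets the endpoint has missed the regimen and so leaves the set. The per-protocol NIV arm then has 0 intolerant patients out of N, whatever the true rate. The dehiscence endpoint tends the same way: Section C counts it only when caused by a total pressure above 20 cmH₂O, and Section D has total pressure kept at or below that value.

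**Step 2. ITT and the NIV-arm rate.** Let h be the harm rate among patients given prophylactic NIV, and u the share of the NIV arm never given it.

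ITT rate = (1 − u) × h

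The arm size is 266 / 2 = 133, and the number exposed is 133 × (1 − u).

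| u (assumed) | Exposed, of 133 | h = 10% | h = 20% | h = 30% | Per-protocol intolerance |
|---|---|---|---|---|---|
| 5% | about 126 | 9.5% | 19% | 28.5% | 0% |
| 10% | about 120 | 9% | 18% | 27% | 0% |
| 20% | about 106 | 8% | 16% | 24% | 0% |

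The relative dilution equals u. It is nil if everyone allocated to NIV receives it.

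**Step 3. Other harms, per-protocol.** Assume that 20% of exposed patients are intolerant, and that a harm such as a skin lesion occurs in 5% of tolerant and 20% of intolerant patients.

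- Among all exposed: 0.80 × 5% + 0.20 × 20% = 8.0%
- Per-protocol (tolerant patients only): 5.0%
- ITT at u = 10%: 0.90 × 8.0% = 7.2%

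**Step 4. Between-arm difference.** The plan expects acute respiratory failure (ARF) in 30% of controls. If half to all of these received curative NIV (assumed), 15–30% of controls would be exposed. At the same 8.0% harm rate:

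- Control rate: 0.15 × 8.0% = 1.2%, to 0.30 × 8.0% = 2.4%
- ITT difference: 7.2 − 1.2 = 6.0 points, to 7.2 − 2.4 = 4.8 points

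This leaves out curative NIV in the NIV arm, which works in the opposite direction.

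**The case against.** The strongest objection is that ITT fits the objective as worded. The plan asks about the safety of a strategy compared between randomised groups. Failure to deliver NIV for organisational reasons is part of that strategy, and any curative NIV in controls is part of standard care. This stands. Harm per exposed patient is a different quantity, and a reader who infers that ITT is wrong goes beyond the documents.

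A reader might also infer that the planned sets always err in favour of NIV, or that the between-arm difference shows some fixed fraction of the true risk. The documents support neither. Treated NIV-arm patients can also develop ARF and receive curative NIV. Take the plan's ARF rates of 15% (NIV) and 30% (control), and assume a 15% harm risk per exposure, independent risks, 90% delivery and curative NIV for every ARF case. The NIV-arm ITT rate is then 0.90 × (0.15 + 0.85 × 0.15 × 0.15) + 0.10 × 0.30 × 0.15 = 15.7%, which is above the 15% risk from prophylactic NIV. The narrowing in step 4 also bears little on intolerance, whose daily target is set for the prophylactic regimen.

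The zero rate can be challenged too. The plan gives no adherence threshold, words the hours as an aim, lets the schedule adapt to unit activity and leaves weaning to the clinician. That is why the claim is put as a plain reading. But adapting to unit activity is not the same as stopping for intolerance, and full adherence is the only rule written.

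Some of the gap may be covered in other ways:

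- The exploratory analyses look at curative versus prophylactic-only NIV, and at factors for failure among early stoppers. The first leaves out of its prophylactic-only group anyone who later needed curative NIV, and the second covers only those who stopped. Neither gives a rate among all who started.
- Section E drops patients whose endpoint is unavailable. If never-NIV patients are coded that way for mask endpoints, the dilution in step 2 largely disappears. The plan does not say so.
- The text is headed as a synopsis and refers to safety assessment parameters under a title that is not visible. A fuller document may say more.

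**Conclusion.** The point holds in two parts of unequal weight.

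1. On the plain reading of Sections C, D and E together, the per-protocol analysis of intolerance returns a rate at or near 0% whatever the truth. This needs no assumed rates. It depends only on missed NIV hours counting as incomplete adherence.
2. ITT remains valid for the strategy as randomised, but it differs from the rate among recipients by the never-treated share: 5–20% in relative terms if 5–20% are never treated, and nothing if all are treated. The true share is unknown. Curative NIV in controls, which the plan neither states nor bars, would narrow the difference for mask-related harms. The net size cannot be fixed from the documents.

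No visible analysis gives a harm rate among all patients who started prophylactic NIV. That is a gap in the analysis populations, not an error in the ITT comparison.

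**What to change.** In Section E, planned statistical methods:

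- State that the NIV safety and tolerability endpoints are not analysed per-protocol.
- Keep the ITT comparison for all harms, and say whether NIV-arm patients who never received NIV count as event-free or as unavailable for mask-related endpoints.
- Add a descriptive safety set of all patients who started at least one prophylactic NIV session. Report each listed event (intolerance, skin lesions, anastomotic dehiscence, gastric distension, mask-related aspiration) as n/N with an exact 95% confidence interval.
- Show events after a first curative NIV session separately, by arm, where timing is recorded. The plan says that conditions are noted at session start. It does not say that each harm is dated against curative sessions, so the case report form should be checked.

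The cost is a few sentences and one extra table. That table is not a randomised comparison and must be labelled so, and the reported harm rates may look somewhat less favourable to NIV. No treatment rule changes.

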- Identification of factors associated with failure of prophylactic NIV in the subgroup where NIV was prematurely discontinued.

Statistical Justification for Sample Size:

Previously described data indicate that the expected effect size is approximately a 50% reduction in events:

- In studies on medical populations, the effect of prophylactic NIV was observed even on harder endpoints than ours: -66% reduction in reintubation, -51% reduction in ARF incidence, and -50% reduction in reintubations, and again -69% reduction in ARF incidence.

- In surgical populations, prophylactic NIV has led to a reduction in restrictive syndrome of about 50%, an improvement in pulmonary function tests (PFTs) of +30%, and a decrease in length of stay by 7 days.
- In curative use after abdominal surgery—a more unfavorable situation since ARF is more advanced—Squadrone reported favorable outcomes in 90% of cases with CPAP, and reintubations were reduced by 30%.

Given that the expected incidence of ARF in the high-risk group is 30–50%, a sample size of at least 121 subjects per arm is required to demonstrate, under a two-sided hypothesis, a relative reduction of 50% in ARF between a group managed with prophylactic NIV (15%) and a group managed with standard care (30%), with an alpha risk of 5% and a beta power of 90%. We anticipate 10% of patients will be non-evaluable.

The required sample size is therefore $242 + 24 = 266$ high-risk subjects evaluated for PPC.

STATISTICAL STOPPING RULES:

No interim analysis is planned in the protocol. However, if during the review of safety and efficacy data provided to the independent monitoring committee (raw, descriptive, and summarized data without pre-established statistics by the investigator or sponsor), a highly significant difference is identified for the primary endpoint or one of the safety parameters when comparing the two groups blinded to treatment allocation, the committee may decide to stop the study.

METHOD FOR HANDLING MISSING, UNUSED, OR INVALID DATA:

Patients included in the study for whom an endpoint is not available will not be considered in the analysis for that missing endpoint. No imputation method will be used for missing data.

MANAGEMENT OF CHANGES TO THE INITIAL ANALYSIS PLAN:

Modifications to the initial analysis plan may be proposed by the monitoring committee (interim analysis, statistical tests, adverse events, secondary objectives) if new literature data justify them.

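### The nine minimisation factors enter no pre-specified comparison of ARF between arms, and the only adjusted ARF model is optional, screened at p<0.20 and reports logistic output as a relative risk

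*Combined protocol and SAP*

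**What the plan says.** The Randomization section specifies "centralized computerized electronic randomization by minimization into two groups (1:1), with stratification by center, sex, age", and continues with preoperative SpO2, recent respiratory infection, anemia, type of incision, expected duration of surgery and urgency. That makes nine factors.

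In section E, the description of planned methods covers the primary comparison by intention to treat and then per protocol. It names no covariates and adds: "Effect size and number needed to treat will be calculated".

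The Study of Associations section gives the test: "The statistical test used will be Pearson's Chi-square test (or Fisher's exact test) for qualitative variables". The bivariate step is "possibly complemented by a multivariate analysis adapted to the outcome variable to explore potential associations". The model itself is then described: "A multivariate logistic regression analysis will estimate the adjusted RR and its 95% confidence interval for each retained factor", with retention governed by a "conservative threshold of 0.20 in univariate analysis".

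Nothing in the text forces the arm or any minimisation factor into that model, and nothing says how an RR is obtained from it. The other adjusted model, a Cox regression under Early Mortality, is for death. The subgroup analyses are exploratory splits.

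**The concern.** There are three linked problems.

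1. **The analysis does not follow the allocation.** Minimisation makes the arms more alike on the nine factors than simple randomisation would. If those factors predict ARF, the difference in proportions varies less from trial to trial than the chi-square variance assumes, so the test rejects too rarely. This cannot produce a false positive, but it gives away power.

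2. **The adjusted model is chosen by the outcome data.** A p<0.20 screen leaves it to the observed results which minimisation factors enter. The plan also wavers on whether the model is run: it is *possibly* added in one sentence and *will* estimate in a later one.

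3. **The label is wrong as written.** For an outcome this common, an odds ratio lies well away from the RR. The plan also reports crude RRs, so a crude RR and a mislabelled odds ratio could appear side by side and the gap be read as an effect of adjustment.

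**Working it through.** **The plan's own sample size.** Inputs from the sample-size section: 30% versus 15%, two-sided 5%, stated power 90%, 121 per arm.

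n = [z(0.975)·√(2·p̄·(1−p̄)) + z(power)·√(p1(1−p1)+p2(1−p2))]² / (p1−p2)², with p̄ = 0.225

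- 80% power: (1.960×0.5906 + 0.842×0.5810)² / 0.0225 = 120.5, so **121**
- 90% power: (1.960×0.5906 + 1.282×0.5810)² / 0.0225 = 160.8, so **161**

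Thus 121 per arm reproduces at 80% power (0.802), not at 90%. This is a separate issue, but it means there is no spare power. Expected events: 121×(0.30+0.15) = 54.

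**Odds ratio against RR.** This step needs no assumption about prognostic strength. The sample-size section states: "expected incidence of ARF in the high-risk group is 30–50" (percent). With a true RR of 0.50:

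- 30% vs 15%: (0.15/0.85)/(0.30/0.70) = 0.412, read as a 59% reduction
- 40% vs 20%: (0.20/0.80)/(0.40/0.60) = 0.375, read as 62.5%
- 50% vs 25%: (0.25/0.75)/(0.50/0.50) = 0.333, read as 67%

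A risk factor with RR 2.0 would read as (0.30/0.70)/(0.15/0.85) = 2.43 from a 15% baseline, and (0.50/0.50)/(0.25/0.75) = 3.0 from 25%.

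**Test size and power.** The documents give no prognostic strength, so four c-statistics were assumed. Factor prevalences and effects are also assumptions.

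- Design: 242 patients, Pocock-Simon minimisation on the nine factors with a 0.9 biased coin, 6,000 runs per setting. Both arms at 30% for type I error; 30% vs 15% for power.
- Adjusted analysis: logistic model with arm, center, sex and a continuous ARISCAT-type score, tested on the standardised risk difference with a sandwich SE. The score was simulated as an imperfect weighted sum of the seven factors other than center and sex.
- Monte Carlo SE: about 0.3 points for type I error and 0.5 for power.

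| Assumed c-statistic | 0.60 | 0.68 | 0.74 | 0.79 |
|---|---|---|---|---|
| Type I error, chi-square (%) | 5.0 | 4.3 | 3.3 | 3.6 |
| Type I error, adjusted (%) | 5.4 | 4.9 | 4.4 | 5.0 |
| Power, chi-square (%) | 79.8 | 81.3 | 81.6 | 83.3 |
| Power, adjusted (%) | 80.7 | 83.4 | 84.5 | 88.4 |
| Gain (points) | 0.9 | 2.1 | 2.9 | 5.1 |
| Mean number of the nine factors kept at p<0.20 | 2.5 | 3.5 | 4.4 | 5.1 |
| Median adjusted OR for arm (true RR 0.50) | 0.40 | 0.38 | 0.36 | 0.33 |

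All nine factors survived the screen in under 1% of runs. The standardised RR stayed at 0.50 throughout.

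The mechanism can be seen at c = 0.74 under the null. The raw risk difference had an empirical SD of 0.0547 against a mean estimated SE of 0.0587. The effective critical value is 1.96×0.0587/0.0547 = 2.10, which implies a two-sided size of about 3.5%, in line with the simulated 3.3%. The spread of the estimate itself hardly changes: SD of log RR unadjusted vs adjusted is 0.264 vs 0.264 at the weakest setting and 0.271 vs 0.266 at the strongest.

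**Checks under other assumptions.**

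- Arm plus all nine factors as categories (0.8 biased coin, 1,500 runs per setting, log-OR per SD of each factor 0 / 0.2 / 0.35 / 0.5): power 81→83, 81→84, 83→88 and 83→92%. Type I error was 4.9 / 4.0 / 2.5 / 3.1% unadjusted and 5.7 / 5.2 / 5.2 / 8.0% adjusted.
- Center, sex and score, different assumed effects (1,500 runs): power 83.2→83.5, 82.5→85.7 and 83.3→89.3%; adjusted type I error 5.3–6.6% (Monte Carlo SE about 0.6 points).
- Center, sex and score, with enrolment truncated on an assumed score: type I error 2.6–5.0% for chi-square and 4.3–6.0% adjusted; gain about 1–4 points.

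**The case against.** The best reply is that the planned test is valid and the gain may be close to nothing.

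- **Source of the gain.** At c = 0.60 chi-square already has a size of 5.0%, and moving alpha to the adjusted test's 5.4% would by itself lift 79.8% to 80.7%. Run at the adjusted test's simulated size, chi-square would have power 80.7 / 82.7 / 84.6 / 86.5%, against 80.7 / 83.4 / 84.5 / 88.4% adjusted. This stands: most of the gain is nominal size restored. Where chi-square runs below 5% that is legitimate; at the weakest setting there is nothing to recover.
- **Restricted enrolment.** Only patients with ARISCAT ≥45 enrol, which narrows the score. For a normal score, enrolling the top half or top fifth (an assumption) turns c = 0.74 into 0.66 or 0.63, and 0.79 into 0.70 or 0.67. The lower part of the range is therefore more plausible, although the truncated simulation still gained about 1–4 points.
- **The score as a stand-in.** The documents mention ARISCAT components but neither list nor weight them, so how well the total score represents the minimisation factors is assumed.
- **The label.** An adjusted RR can be derived from a logistic model by standardisation, and the sentence concerns risk factors without saying that arm is included. Both are true. But no such method is named, and the distortion affects risk factors just as it affects arm.
- **Synopsis only.** The available text is headed as a synopsis, so the gap is established for that text only.

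**Conclusion.** The concern holds, at moderate weight. In the available text no between-arm analysis of ARF is required to use any minimisation factor, and the only adjusted ARF model has an uncertain status and data-chosen covariates.

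The label error is the firmest part, because it follows by arithmetic from the plan's own incidence range. The cost of the unadjusted test is small, uncertain and on the conservative side: nil to a few points of power, depending on a prognostic strength that the documents do not give. The primary crude RR and the NNT remain correct. This is an inexpensive improvement to a valid analysis, together with a correction of wording that is wrong as it stands.

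**What to change.** Before any outcome data are seen, and with no trigger based on observed events, specify one between-arm analysis of committee-validated ARF:

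- Fit a logistic model with arm forced in and a small fixed covariate set, for example center, sex and the continuous baseline ARISCAT score, with no p-value screening.
- From that model report the marginal risk difference (as the test) and the marginal RR by standardisation, each with a robust 95% CI.
- Keep chi-square/Fisher with the crude RR as a sensitivity analysis.
- In the exploratory risk-factor models, label logistic coefficients as odds ratios or convert them by a named method. State plainly whether those models will be run.

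The cost is plan wording and minor programming. The score is already needed for eligibility, and center and sex for allocation.

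The downside is more parameters on about 54 events. The example set has 6 (intercept, arm, two for center, sex, score), or 54/6 = 9 events each. Entering all nine factors with age and SpO2 continuous takes 14, or 54/14 = 3.9 each. Its type I error was 4.7–5.7% in the main simulation, but the all-categorical version reached 8.0%, so the full set is not advised. Modified Poisson regression on the small set is also valid (type I error 4.2–4.9%), but it changes power by only −1 to +3 points.
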